#### Future Use of Data and/or Biospecimens.

Participants will be given the option to let us store their biospecimens (blood and urine) and information for use in future research. This storage may be for an indefinite amount of time. The information and samples provided may be shared with other research institutions, e.g. The Abramson Cancer Center at Penn, or researchers working with the NIH who want to learn more about nicotine addiction and/or better ways to help people quit smoking. Whole genome sequencing will not be conducted on samples. We will protect participant confidentiality by first labeling their information and samples with an identification number only (not their name). We will restrict access to the databases that hold their personal information. Their samples will be stored in a locked, private bank, which only authorized personnel will have access to. Permission to store their information and samples for use in future research is optional and they will indicate their choice at the end of the consent form. Participants may withdraw their permission at any time by contacting study staff and letting us know they no longer want their information and samples to be stored for use in future research. Participant samples may be used to create products, including some that may be sold and/or make money for others. If this happens, there are no plans to tell the participant, or to pay them, or to give any compensation to them or their family. Additionally, we will not follow up with participants about the specific research that will be done, and individual research results obtained as part of future research will not be shared with them.

#### **5. *Tissue Specimens***

##### Blood.

Two samples (one 10 mL and one 8 mL) of blood will be drawn at the Intake visit to evaluate the nicotine metabolite ratio and neuroinflammatory markers. All specimens are to be collected solely for research purposes. For participants who must have their HIV status confirmed on-site, a finger-prick rapid blood test will be completed at Intake visit. Participants who attend visits at the Bradbury-Sullivan Center will not undergo a blood draw, and will only be HIV-positive, therefore no rapid test will be conducted.

##### Urine.

A urine sample will be required at the Intake Session, Lab Session 1, and Lab Session 2 for drug screenings. Subjects who test positive for study prohibited drugs will be deemed ineligible. All female participants of child-bearing potential will complete urine pregnancy tests. Approximately 8mL of the urine collected for drug screen will be stored to evaluate nicotine metabolites, unless the visit is conducted at the Bradbury-Sullivan Center, where storage will not be possible. This will be for research purposes only.

#### **6. *Genetic Testing***

N/A

### **RISK/BENEFIT ASSESSMENT**

#### **1. *Potential Study Risks***

A detailed description of the study will be given to all subjects, which will include the risks of participation, assurance of full confidentiality, and the knowledge that their freedom to refuse participation or withdraw from the project will not

affect the availability of treatment at the University of Pennsylvania. Informed consent procedures will comply with current standards of the IRB at the University of Pennsylvania. Subjects can choose, as an alternative, to not enroll in this study. Adverse reactions will be assessed and reported as required by Federal law and the regulations of PENN.

**Blood Draw.** Blood draws may result in bruising and/or slight bleeding at the needle site. This is rare and happens infrequently. Occasionally, blood drawing results in a feeling of faintness. This too is rare. A trained professional will draw blood, so the chances of these discomforts are minimal. Procedures are in place to ensure that PHI is not linked with the results of this research.

**HIV Testing.** Rapid HIV blood testing may result in mild pain from the finger stick and feelings of anxiety about HIV status results. Staff members administering HIV tests will be trained to provide counseling and recommendations for continued care to participants should they receive a positive result.

**Assessments.** Subjects may experience emotional distress during assessments from discussing feelings and attitudes about smoking or from learning about the risks from smoking. These events happen very rarely and in almost all cases are short-lived and of low intensity, lasting for 1-2 weeks. Study personnel will be alerted to expect this from a small number of subjects and will be trained to make referrals for mental health services as needed. Personnel will be trained to query for adverse emotional reactions during assessments and will be trained to deal with such reactions and to provide additional referrals if needed. In addition, if assessments indicate psychiatric concerns, referrals to appropriate psychological services will be provided.

**Transdermal Nicotine (TN) Replacement Therapy.** All participants will receive transdermal nicotine (TN) patch therapy to aid in quitting smoking. This therapy is available over the counter and is very well tolerated. Nausea, vomiting, weakness, dizziness, and rapid heartbeat occur rarely and are most often caused by continuing to smoke while using the patch. In some cases, nicotine patch use may delay wound healing and may contribute to the risk of peptic ulcer formation. Some individuals who use the patch experience minor skin irritation, such as redness, rash, or minor swelling, and insomnia and dream abnormalities. Sleep problems are a primary mechanism of interest. Participants who experience insomnia and/or dream abnormalities may be instructed to remove the patch during the night while sleeping. Symptoms of an allergic reaction may include difficulty breathing or rash. All of these reactions cease once the patch is removed.

During the pre-quit counseling visit (week 3), the counselor will review the purpose of using the nicotine patch (e.g., to help manage withdrawal symptoms; not a substitute for behavioral quitting strategies), provide directions on how to use the patch (e.g., abstinence from smoking, patch location, time, activity, and potential skin reactions), and answer any questions.

Increased blood pressure and heart rate are possible side effects of TN patch therapy. Blood pressure will be closely monitored at the Intake and Lab sessions prior to the treatment phase. Expanding the upper limit of the blood pressure to less than 160/100 does not increase the risk to subjects enrolled in this trial. The risk of increased blood pressure is no greater than the risk from smoking and quitting smoking will lower an individual's risk. Irregular or rapid heartbeat and palpitations will also be screened for at each visit in the treatment phase.

Participants will complete a patch side effects checklist at each visit. Staff/the PI will review the checklists for serious and persistent side effects. These will be communicated immediately to the study physician. Participants will be instructed to promptly discontinue the patch and contact the SP/PI if they experience severe or persistent local skin reactions (e.g., severe redness, itching, or swelling) at the site of patch application or a generalized skin reaction (e.g., raised patches, hives, or generalized rash). Any serious adverse reactions or significant side effects of TN will be medically evaluated by the study physician. Patch use by such individuals will be monitored and adjusted as needed. Based on our previous experience with NRT studies (Lerman et al., 2004; Schnoll et al., 2010), we expect few serious adverse events. Nevertheless, the study physician will be available to assist with any adverse events and participant safety issues.

Depending on the nature of the side effects the study physician may reduce the dose of the patch or recommend that the participant discontinue the patch.

**Reproductive Risks.** Because transdermal nicotine safety for an unborn baby is unknown, participants will be told that they should not become pregnant while in this study. Women in the study should not nurse a baby. If the woman is of childbearing potential, she must use an adequate form of contraception or abstain from sexual intercourse for the duration of the study. If the woman is pregnant or breast feeding, she may not participate in this study, and if she becomes pregnant during the study, transdermal nicotine will be immediately discontinued and the subject will be permitted to continue with counseling and assessments only. Women will be asked to take a pregnancy test at the intake session, as well as laboratory sessions 1 and 2.

**Withdrawal Syndrome.** Many individuals who quit smoking exhibit a pattern of symptoms related to withdrawal from tobacco use. These symptoms include sadness and anxiety, irritability, anger, difficulty concentrating, appetite change and weight gain, insomnia, and decreased heart rate. Eliminating the risk for these would not be possible, although in most cases these events are short-lived and have low intensity, lasting for 1-2 weeks. The study personnel will be trained to recognize these symptoms and educate the participants about them (e.g., their duration, methods for reducing them).

**Non-invasive Rhythm Monitoring Device Risks.** Based on extensive clinical and research experience, there are very minimal risks of 14-day ECG monitoring using the rhythm monitoring device. Mild skin irritation from the device and feelings of anxiety engendered by the knowledge that their cardiac rhythm is being monitored are possible. Any arrhythmia that occurs during the wear period will be evaluated at the time the device is analyzed. As noted above, [name] will review all iRhythm reports including the rhythm tracings and, along with [name], will contact any participant with 1) wide QRS tachycardia > 120 beats per minute (bpm) and sustained for > 30 seconds, 2) complete heart block, 3) sinus pauses > 3 seconds, 4) bradycardia less than 40 bpm and sustained for > 30 seconds, 5) AF/atrial flutter with average heart rate less than 40 bpm or > 180 bpm and sustained for 60 seconds, 6) narrow QRS tachycardia > 180 bpm and sustained for 60 seconds. If clinically warranted, [name] will refer participants to the Penn Arrhythmia Center for more formalized clinical assessment.

**Potential Loss of Confidentiality:** Every attempt will be made by the investigators to maintain all information collected in this study strictly confidential. We will store subject information in a secure room with limited access. Only people working on this research project can access subject information. We will control access to the computer files that hold this information. This information will not be released to anyone. When the results of the study are published, no names or identifying information will be used.

## **2. Potential Study Benefits**

All participants who enroll in this study will receive behavioral counseling to aid them in their effort to quit smoking. They may also benefit from the knowledge that they are contributing in an important way to potentially furthering scientific knowledge concerning ways to improve cessation treatment for smokers.

## **3. Alternatives to Participation**

As an alternative to enrolling in this study, participants may choose to continue to smoke or to seek assistance with quitting smoking through other treatment programs located in their area, including contacting the national quit-line. At any point in this trial, subjects may decide not to continue in their participation.

## **4. Data and Safety Monitoring**

Who will monitor this study? Check all that apply.

Principal Investigator

Sponsor or contract research organization

- NCI sponsored cooperative group
- Cancer Center (if mandated by CTSMRC)
- Medical monitor
- Safety monitoring committee
- Data and safety monitoring board

Data and Safety Monitoring will be conducted by the Principal Investigators and the Study Physician. They will review all possible Adverse Events (AEs) and Serious Adverse Events (SAEs). They will ensure that this information is captured in a comprehensive manner and reported according to Good Clinical Practice (GCP). The Principal Investigators, Study Physician, and the research staff will oversee and complete the monitoring process. Monitoring will be performed on an ongoing basis in accordance with the University of Pennsylvania Sponsor-Investigator Standard Operating Procedure PM 004.

The Principal Investigators are responsible for:

1. Obtaining IRB review and approval of a clinical investigation before the investigation is initiated and ensuring continuing review of the study by the IRB in accordance with 21 CFR Part 56;
2. Obtaining informed consent in accordance with 21 CFR Part 50; and
3. Assuring that all staff and subjects understand and accept the obligations incurred in undertaking this study in accordance with 21 CFR Parts 812, 813 and any other applicable regulations.

The research staff is responsible for collecting and recording all clinical data. This includes ensuring that all source documents exist for the data on the Case Report Forms (CRFs), ensuring all fields are completed appropriately, and all corrections are done according to GCPs. Any inconsistencies/deviations will be documented on the CRFs and such findings will be reviewed at the weekly study meetings.

The Project Manager will oversee staff training. Training will include a review of the study protocol, informed consent, telephone screen, CRFs and the procedures that are in place regarding session check-in, data collection, data entry and quality control. All applicable regulations will be reviewed and the roles/responsibilities of each staff member will be explained. All questions will be answered and the training will be documented in a training log, which will be initiated by those involved. The Project Manager will also confirm all appropriate documentation of informed consent and storage of consents in a separate consent binder, and will maintain the study regulatory binder.

The Project Manager, PI, and Study Physician will work together to confirm eligibility criteria. The PI/PM will review charts for each subject to confirm eligibility and will document this review by signing/initialing and dating the final eligibility checklist in each chart.

The data managers will be responsible for creating all CRFs and ensuring that all data will be entered and stored in a manner consistent with the design of the approved CRFs. They will also be responsible for developing the data entry/quality control producers for this study.

- a. Enrollment will be complete when 300 subjects (150 HIV+ and 150 HIV-) complete all study requirements. On average, 6 subjects will be enrolled per month. During the course of the study, safety and data quality monitoring will be performed on an ongoing basis in accordance with the University of Pennsylvania Sponsor-Investigator Standard Operating Procedure PM 004 and any findings will be reviewed on a regular basis with the Investigators at the regular study meeting. The monitoring will include a regular assessment of the number and type of serious adverse events. The first monitoring day will occur no more than two weeks after the first subject is entered.

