### **2. Accrual**

For this trial, we project that we will screen about 1200 smokers over 63 months (allowing six months to complete follow-up). Based on our varenicline trial with HIV-infected smokers (IRB Protocol #815435) and the present inclusion/exclusion criteria, we expect about one-third of these smokers to be eligible for the trial (n = approximately 415). To be conservative, given the possible health problems evident in this population of smokers, we will project less than 25% of participants will withdraw from the trial and more than 75% of subjects will complete follow-ups to have 300 complete the study. As is advised in smoking cessation trials (Hughes et al., 2003), intent-to-treat will be used for primary analyses, with missing outcome data coded as smokers.

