#### 2. Design

**Main Study.** This study will use a prospective observational matched-design to test whether HIV+ smokers (vs. HIV-smokers) are more likely to experience cognitive deficits during nicotine withdrawal and whether these deficits are predictive of smoking relapse. As shown in Figure 1, adult treatment-seeking smokers (N=300; 150 HIV+ and 150 HIV-) will complete this 12-week study, which is divided into two phases: a pre-quit laboratory phase (weeks 0-2) and a treatment phase (weeks 3-12). Subjects will complete two laboratory sessions during the pre-quit phase: once following 24 hours of mandatory smoking abstinence and once while smoking-as-usual (order counter-balanced; abstinence biochemically confirmed). A cognitive task battery assessing working memory, sustained attention, and response inhibition will be administered during each session. During the treatment phase, subjects will receive standard smoking cessation treatment, including six sessions of brief individual counseling (weeks 3-8) and eight weeks of open-label transdermal nicotine (TN) patch treatment (weeks 4-12) [34]. The primary outcomes will be: 1) cognitive performance (e.g., verbal and working memory) following 24-hours smoking abstinence (vs. smoking-as-usual) during the pre-quit phase, and 2) 7-day point-prevalence, biochemically confirmed abstinence rates at end-of-treatment (EOT) for the treatment phase. Since randomization is not possible in this study, we will rely on inclusion criteria and matching to reduce the potential for confounding. More specifically, participants will be

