#### Projected date of completion of the proposed study

We expect to complete accrual in approximately 63 months, with visit completion by June 2022. We expect to obtain our numbers in this timeframe by enrolling approximately 6 subjects per month.

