## 2. Statistical Analysis

### **Power Analysis and Sample Size.**

Our study is a longitudinal between-subject design that seeks to test the following hypotheses: 1) that HIV+ smokers experience larger abstinence-induced cognitive deficits than HIV- smokers (Aim 1); 2) have lower quit-rates than HIV-smokers following standard treatment (Aim 2); and 3) that the association between HIV status and relapse is mediated by abstinence-induced cognitive deficits (Aim 3). We have designed our study to achieve 80% power, testing at a global  $\alpha=0.05$  for each of the hypothesis families (Figure 1). Our sample size of 300 was determined primarily by Aim 2. Based on prior work, we expect a ~15% difference in abstinence rates between HIV+ and HIV- smokers (Ferketich et al., 2013; Humfleet et al., 2013; Matthews et al., 2013; Silagy et al., 2004). With 150 HIV+ vs. 150 HIV- smokers, we have 80% power to detect a difference of ~15 percentage points in point-prevalence abstinence (60% vs. 45%, 50% vs. 35%, 40% vs. 25%), using a z-test on log-odds with a type 1 error of 5%. For Aim 1, we will test the HIV status by abstinence condition (24-h abstinence vs. smoking-as-usual) interaction for 5 cognitive measures using a linear regression with one between- and one within-subjects factor. We will correct for 5 tests using  $\alpha=0.01$ . We have 80% power to detect medium effect sizes (Cohen's  $d=0.4$ ). For Aim 3, we will test whether abstinence-induced cognitive deficits predict quit rates and, using SEM, test whether cognitive deficits mediate the effect of HIV status on quitting. The primary aim will be to test the overall fraction of the effect mediated, which will be tested at  $\alpha=0.05$ , which gives 80% power to detect small to medium effects ( $d=0.32$ ). For our exploratory aim, the component individual deficits will be treated as secondary and tested individually as part of an exploratory analysis, also with a 5% type 1 error. To characterize cognitive deficits in HIV+ smokers, 150 subjects will give us an estimate for each measure with a 95% CI that is 0.32 standard deviations wide (Upper – Lower limits). We will estimate the within-subject correlation for these as repeated measures, with a 95% CI that is 0.32 wide (Upper – Lower) if  $r=0$ , 0.24 if  $r=0.5$ , and 0.14 if  $r=0.75$ . Power was calculated using PASS software, NCSS, Kaysville, UT.

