### **Data Analysis.**

[name] will conduct analyses using Stata, SAS, or R-Language software. Preliminary analyses will determine whether data meet distributional assumptions, and use appropriate transformations where they do not. We will also determine whether subject characteristics (e.g., gender, nicotine dependence, depression, NMR) are associated with HIV status or outcomes using either cross-tabulation (chi-square), *t*-tests, or correlations. Variables showing potential to predict outcome ( $p=0.2$ ) will be tested for entry as controlling variables. In the event of items missing at random on survey measures, missing items will be imputed prior to calculating final scores using conditional means, estimated with an iterated version of Buck's method (Gleason and Staelin, 1975). Dropout and missed sessions present a more serious issue. The best way to deal with this more serious missing data is to avoid the problem in the first place by keeping subjects connected to the trial and motivated to complete measures. Our clinical trials have a record of >80% compliance and retention rates, thanks to our monitoring of participants and use of incentives to offset costs for travel. Primary analyses will include all subjects who went through the laboratory phase and began NRT treatment; we will assume those who provide incomplete smoking data are smoking. This assumption is the convention in smoking cessation research, but can attenuate the differences between study groups. We will, in addition, conduct analyses with other missing data assumptions, including a completers only analysis, to examine the sensitivity of the primary findings to our assumptions.

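### The 80% power for Aim 2 is not met at 150 per group for two of the three listed rate pairs, and it is not tied to the primary analysis set

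*Combined protocol and SAP*

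**What the plan says.** The number 300 is a count of completers. Data and Safety Monitoring (section 4) says "Enrollment will be complete when 300 subjects (150 HIV+ and 150 HIV-) complete all study requirements". Design says that "adult treatment-seeking smokers (N=300; 150 HIV+ and 150 HIV-) will complete this 12-week study", and Accrual plans for fewer than 25% withdrawing so that 300 finish.

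Power Analysis and Sample Size uses the same number as the size of the comparison: "Our sample size of 300 was determined primarily by Aim 2", and "With 150 HIV+ vs. 150 HIV- smokers, we have 80% power to detect a difference of ~15 percentage points in point-prevalence abstinence". The rate pairs and the test are given as "60% vs. 45%, 50% vs. 35%, 40% vs. 25%), using a z-test on log-odds with a type 1 error of 5"%. The section does not say whether the test is one- or two-sided, whether 150 per group means completers or people analysed, or whether the rates count missing data as smoking.

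The primary analysis is wider than completers. Accrual says "intent-to-treat will be used for primary analyses, with missing outcome data coded as smokers". Data Analysis defines the set: "Primary analyses will include all subjects who went through the laboratory phase and began NRT treatment", with incomplete smoking data again taken as smoking. It accepts that this rule can shrink the group difference, and it adds a completers-only analysis as a sensitivity check. The primary abstinence endpoint, under Outcomes Variables, treats anyone who cannot be reached or gives no breath sample as smoking.

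**The concern.** The power figure that sized the trial raises two questions. The first is whether 80% follows from the stated inputs at all. The second is whether 150 per group, a completer count, is the right size for a primary analysis that also includes people who began treatment and then withdrew. Adding them raises the number analysed. It could also shrink the difference, if the assumed rates were meant for completers.

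The stake is how the Aim 2 result is read, above all a null one: a reader needs to know what power the primary test had. Aim 3 is affected too, because the mediation analysis is planned on the assumption that Aim 2 shows a significant effect of HIV status.

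**Working it through.** **Inputs.** From Power Analysis and Sample Size: 150 per group, pairs 60/45, 50/35 and 40/25, z-test on log-odds, type 1 error 5%. From Accrual: withdrawal below 25%. Assumed: a two-sided test.

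**Formula.** With n per group and q = 1 − p: d = logit(p1) − logit(p2); SE² = 1/(n·p1·q1) + 1/(n·p2·q2); power = Φ(d/SE − 1.96).

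**Step 1. The plan's own figure, n = 150.**

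- 60/45: d = 0.606; SE = √(1/36 + 1/37.125) = 0.234; d/SE = 2.59; power = Φ(0.63) = 74%.
- 50/35: d = 0.619; SE = 0.237; d/SE = 2.62; power = 74%.
- 40/25: d = 0.693; SE = 0.252; d/SE = 2.75; power = 79%.

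Only 40/25 comes close to 80%. Other variants do not rescue the statement. A pooled z-test on proportions gives 74%, 75% and 80%; an unpooled one 75%, 76% and 80%; a continuity-corrected one about 70%, 71% and 76%. A one-sided log-odds test gives 83%, 83% and 87%. None gives 80% for all three pairs.

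Solving for n at 80% power, n = (1.96 + 0.842)² × [1/(p1·q1) + 1/(p2·q2)] / d², gives 176, 172 and 156 per group. Put as a detectable difference at 150 per group (pooled test), 80% power needs about 16 points above a lower rate of 45% or 35%, and about 15 points above 25%.

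**Step 2. Size of the primary analysis set.**

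- Enrolment needed for 300 completers at 75% retention: 300/0.75 = 400, or 200 per group. This is an upper end, because people lost before starting nicotine replacement are excluded from the primary set, not coded as smokers.
- If half of that loss comes before treatment starts (an assumption): 400 − 50 = 350, or 175 per group.
- With no loss after treatment starts: 300.

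**Step 3. Power at 175 and 200 per group under two readings of the rates.**

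Reading A: the listed rates already count missing as smoking, so they apply unchanged to the larger set. Reading B: they are completer rates, so each is multiplied by the completing fraction, 150/175 = 0.857 or 150/200 = 0.75, taken as equal in both groups. The 15-point difference becomes 12.9 or 11.25 points.

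| Pair | n = 150 as listed | A, n = 175 | A, n = 200 | B, n = 175 | B, n = 200 |
|---|---|---|---|---|---|
| 60/45 | 74% | 80% | 85% | 67% | 63% |
| 50/35 | 74% | 81% | 86% | 70% | 67% |
| 40/25 | 79% | 84% | 89% | 76% | 74% |

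Under reading B, unequal dropout between the groups would move power in either direction.

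**The case against.** The strongest reply is that the mismatch probably helps the trial. The power statement speaks of point-prevalence abstinence, and the endpoint section defines that outcome with unreachable participants counted as smokers. Reading A is therefore the natural one, and an analysis set larger than 300 then raises power to 80% or more at 175 per group. This stands. A reader might infer from the table that the primary test has only about 63% power, but that needs reading B, which the endpoint definition does not favour, together with the largest post-treatment loss.

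A second reply is that the plan says only approximately 15 points, and 16 is close. That is fair as to size, but the plan lists exact pairs and attaches 80% to each. The Background rates for nicotine patch (30% in the general population, 10-15% with HIV) also soften the matter: 30/15 gives 86% at 150 per group, and 84% even under reading B at 200. The power statement, however, does not list that pair.

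Three stronger readings are tempting and fail.

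- A reader might say that the 80% describes no planned analysis. The completers-only sensitivity analysis has 150 v 150 under the stop rule, so the figure has a home there if the rates are completer rates.
- A reader might say that accrual cannot reach the stop rule, since 6 × 63 = 378 enrolled gives 284 completers at 75%. But 75% is a floor, and Data Analysis cites a record above 80%. Only 300/378 = 79% is needed. The text is also approximate ("We expect to obtain our numbers in this timeframe by enrolling approximately 6 subjects per month").
- A reader might call the 415 eligible an error, because a third of 1200 is 400. The text says about one-third, and 415/1200 is 34.6%.

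**Conclusion.** The point holds in two parts. First, with a two-sided 5% test the stated 80% is about 74% for two of the three listed pairs and 79% for the third, whichever set the 150 per group denotes. This rests on the unstated sidedness; a one-sided test would put all three above 80%. Second, the figure is not tied to the primary analysis set, whose size lies between 300 and about 400.

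Within each pair the open question of rate scale moves power from 63-67% to 80-85%, from 67-70% to 81-86%, or from 74-76% to 84-89%. These ranges assume 175 to 200 per group and equal dropout. The higher range is the better supported, so the documents do not show that the primary test is underpowered. They show a sizing figure that is wrong as written for two pairs and unlabelled for the analysis that matters.

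**What to change.** In Power Analysis and Sample Size:

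1. State that the test is two-sided (or otherwise), and that the abstinence rates count missing data as smoking, in line with the endpoint definition.
2. Give the expected size of the primary analysis set, meaning those who complete the laboratory phase and begin nicotine replacement, not all enrolled.
3. Restate power for each listed pair at 150 per group and at that expected size. Label the 150 v 150 row as the completers-only sensitivity analysis, and note that it takes the pairs as completer rates.

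Leave the target of 300 completers and the accrual text as they are. The cost is a few sentences and a small table, with no added participants and no change to conduct.
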